## 5.2 Primary outcomes measure(s)

### ***Clinical evaluation of the OLO (Sight Diagnostics) system:***

- Neutrophil count from OLO (Sight Diagnostics) system and standard laboratory test full blood count (FBC).

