## 5.3 Secondary outcomes measure(s)

### ***Feasibility of recruiting patients and use of the OLO (Sight Diagnostics) system:***

- Proportion of those recruited from those consented and/or approached
- Proportion of recruited participants with a valid (as opposed to an invalid test result) from all recruited participants. A valid result is when the OLO system neutrophil result is  $\pm 0.2 \times 10^9/L$  of the laboratory gold standard result;
- Proportion of recruited participants returning the follow-up survey from all recruited participants;
- Number and type of OLO System (Sight Diagnostics) device flags and error codes raised during device operation for fingerprick versus venous blood sample to assess device accuracy;
- Number of re-takes of finger prick versus venous blood sample to assess device accuracy.
- Number of cases in which a discrepancy between the OLO System and gold standard would change the management of the patient, according to retrospective clinical review.
- Number of patients with valid OLO System test results for:
  - Haemoglobin – (validity  $\pm 0.7$  g/L)
  - Platelets – (validity  $\pm 15 \times 10^9/L$ )
  - Lymphocytes – (validity  $\pm 0.3 \times 10^9/L$ )

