### 6.1.1 Cohort selection

A healthcare worker discussion group meeting held at VCC in April 2019 identified three local areas to explore for use of the OLO (Sight Diagnostics) System in the management of cancer patients:

[figure not shown]
1. Acute admissions between 09:00 and 17:00, supported by Acute Nurse Practitioners and/or Acute Oncology Staff (AOS)
2. Acute admissions out of hours and weekend, supported by Senior Hours Officers (SHOs) and the nursing team
3. Pre-chemotherapy checks of patients who have presented with 'borderline' neutropenic (WBC counts) prior to or on the day of chemotherapy, supported by Phlebotomists.

The staff groups managing these areas vary dependent on whether the patient presents as an acute admission during normal working hours or out of hours and weekend. Similarly, the location of processing of whole blood samples collected during this process, and the gold standard equipment varies dependent on if the patient presents at clinic during or outside of routine local clinic and sample analysis hours. Routine samples collected from patients between 09:00 and 16:00 Monday to Friday will be analysed locally at the VCC Laboratory. Routine samples collected outside of these hours during the evening and/or weekend will be transported to the Cardiff & Vale Health Board Laboratory Service at a separate location (Heath Hospital site, Cardiff) for testing.

Taking these local aspects into account, the discussion group concluded that areas 2 and 3 were most likely to be deliverable locally with maximum impact due to limited availability of some staff groups and logistics of moving device equipment between different locations and teams. Therefore, this feasibility study will investigate two patient cohorts:

**Cohort 1: Suspected neutropenic sepsis:** Patients who, following UKONS assessment via telephone triage have been asked to attend the clinic for further assessment for suspected neutropenic sepsis, and present as an acute admission out of hours and at weekends (Figure 5)

**Figure 5.** Routine patient management pathway for suspected neutropenic sepsis in patients receiving chemotherapy

**Cohort 2:** ‘Borderline’ neutropenia: patients with an inconclusive ‘borderline’ neutrophil count at their pre-chemotherapy assessment who require a repeat test prior to receiving chemotherapy on the planned day of chemotherapy (Figure 6.).

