### **11.2 WP1 standard comparator system**

The standard whole blood analyser system used in the central Cardiff & Vale Laboratory at University Hospital Wales, Cardiff is the Yumizen 1500 and 2500, and at the satellite laboratory at VCC, Whitchurch, the Horiba Pentra DS120 or similar. These devices are automated high throughput systems capable of approximately 100 tests/hour using approximately 100-200µl sample volume and an autoloader. The systems test for multiple parameters including a 5-part WBC count and require an experienced operator. These systems will be used as the comparator system for evaluation of the OLO System in this trial and will be operated by the routine operator.

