## 12 Trial procedures

### 12.1 WP1: Cohort comparator study

#### 12.1.1 ..... WP1 screening assessments

On average we anticipate participants will participate in WP1 for a period of up to one month from the date of registration to the end of trial follow up. There will be no cost to the participant for participating in the trial. Participants will not be paid for participating in the trial. The participant will not be required to have any additional medical checks or medication, or attend the hospital more frequently, during the course of the study than they would if they do not participate.

The Participant must not be given the relevant WP1 PIS/ICF until after the routine non-trial assessments, treatment and sample collections for the relevant cohort have been completed as specified in Section 9.

After taking written informed consent, but before registering a patient in the study, the patient's healthcare professional will collect some screening information to confirm they are eligible to take part in the study (See Section 9.4).

#### 12.1.2 ..... WP1 trial-specific blood sample collection

Following registration, the following study blood samples will be collected from each participant for testing using the investigational device from participants recruited to Cohort 1 or 2:

1x 30µl new study sample of whole blood collected using the finger prick method and a Prolance Max Flow Lancet (or suitable locally or externally sourced alternative) and transferred to a OLO (disposable cartridge using the method described in the OLO System Operating Manual (i.e. 1 replicates).

OR

1x 700µl new study sample aliquot taken from a previously collected routine K2EDTA venous blood tube sample using the blood tube dispensers provided.

A second study sample (new fingerprick or existing venous sample aliquot) will be collected if the original study sample results in a test result error.

Study samples will be tested using the OLO (Analyser following the instructions provided in the OLO- Operating Manual [31], before the participant is discharged from hospital. The test result will be obtained <10 minutes after inserting the microcuvette into the analyser.

Consent and sample collection must be initiated as soon as possible after completion of the standard non-trial assessments, treatment and sample collections.

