Study samples must not be removed from routine venous samples until the sample has stood for **at least 20 minutes**. If this process will prevent the routine sample from reaching the routine laboratory within the required local and/or national permitted timeframe a finger prick sample must be taken instead.

Samples tested in the OLO (Sight Diagnostics) analyser will be destroyed following local hospital procedures immediately following conduct of the study test. The samples will not be stored for future research.

The participant and their treating hospital consultant will only be told the results from their standard care tests. The result from the study tests will **not** be used to manage the participant.

If the standard care test(s) show that the participant has neutropenic sepsis their treating hospital consultant will decide what treatment they need (for example whether or not they need to continue taking antibiotics, stay in hospital, or can be discharged) in discussion with the participant and following local standard procedure.

### **12.1.3 .....ADVANCE Qualitative Acceptability Survey**

Prior to discharge from the hospital, Cohort 3 participants will be given a paper copy of the ADVANCE Survey [33] to complete about their views around the study and our intended use of the new equipment

The healthcare professional will ask the patient to complete the survey before they leave the hospital following their discharge. The survey will take about 30 minutes for the participant to complete. Completed surveys will be handed to the local PI.

**12.1.4 ..... Baseline toxicity data**

Baseline toxicity data will be collected after consent and prior to collection and analysis of study blood samples. SAEs must be reported following the timeframes and procedures specified in Section 13.

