## **14 Statistical considerations**

### **14.1 Sample size**

#### **14.1.1 WP1 Device cohort study**

##### **Cohorts 1 and 2 combined:**

We will evaluate the concordance between the OLO neutrophil result and the standard of care laboratory result from the same time period, across all patients with a valid output. A valid OLO neutrophil result will be one which produces a test result which is within  $\pm 0.2 \times 10^9/L$  of the standard laboratory result.

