## **14.2 Missing, unused & spurious data**

The OLO ( System Operating Manual describes the expected white blood cell values for normal adults

The values may vary due to a wide range of factors, such as sex, diurnal variations, exercise, physical stress or trauma, pregnancy, indigestion of food, and cigarette smoking. The OLO-U1 Analyzer automatically assesses the OLO result against one of two pre-defined ranges (female age 22 years+ or male age 22 years+) and flags values outside of these normal values.

When capillary skin puncture is performed, several defence systems in the body are activated very quickly. These defence systems cause an increase in the number of WBCs in the blood closest to the wound, leading to greater differences in results from several samples taken from the same finger stick.

The participating sites normal laboratory ranges for a white blood cell and differential blood count will be sent to the CTR during site set up and will be taken into account when analysing the trial data.

For the purpose of ADVANCE the OLO-U1 Analyser will be programmed to compare the results against these standard local lab ranges for adult males and females.

A detailed Statistical Analysis Plan (SAP) [36] will be in place prior to the main trial database lock and analysis.

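### The neutrophil concordance pools venous-aliquot and finger-prick pairs in an unfixed mix; agreement and validity should be reported by sample type

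*Protocol*

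**What the plan says.** The primary outcome (section 5.2) is the neutrophil count from the OLO and from the laboratory full blood count. The outcome definition does not mention sample type. Section 14.1.1, under the heading for Cohorts 1 and 2 combined, says: "We will evaluate the concordance between the OLO neutrophil result and the standard of care laboratory result from the same time period". That analysis covers patients with a valid output, and a valid output is one within ±0.2 × 10⁹/L of the laboratory value.

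The other relevant provisions are these:

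- **Sample type.** Section 12.1.2 allows a new finger-prick sample or a "new study sample aliquot taken from a previously collected routine" venous tube. The tube must first stand for at least 20 minutes. If that would stop the routine sample reaching the laboratory "within the required local and/or national permitted timeframe a finger prick sample must be taken instead". No other rule governs the choice, and no target split is given. Section 6.1.1 still describes a finger-prick sample only, for both cohorts.
- **Capillary effect.** Section 14.2 says of skin puncture: "These defence systems cause an increase in the number of WBCs in the blood closest to the wound, leading to greater differences in results".
- **Reference analyser.** Section 6.1.1: "Routine samples collected from patients between 09:00 and 16:00 Monday to Friday will be analysed locally at the VCC Laboratory". Samples taken at other times go to the Cardiff & Vale laboratory. Section 11.2 gives the analysers at the two laboratories as "the Yumizen 1500 and 2500, and at the satellite laboratory at VCC, Whitchurch, the Horiba Pentra DS120 or similar".
- **Operator.** Section 11.3 assigns Cohort 1 samples to senior house officers or nurses, and Cohort 2 samples to phlebotomists.
- **Comparison by sample type.** Section 5.3 plans this for flags and error codes, and as "Number of re-takes of finger prick versus venous blood sample to assess device accuracy". It does not plan it for neutrophil agreement.
- **Use of validity.** Table 7 in section 15.1 sets a valid result in at least 90% of tested participants as the intervention fidelity criterion.

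**The concern.** The two permitted samples answer different questions. With a venous aliquot, the OLO and the laboratory measure the same blood, so a difference reflects the analysers and the handling of one tube. A finger prick is a different specimen drawn later: section 12.1.2 places it after routine sampling and treatment, and Table 2 places Cohort 1 consent after antibiotics have started. A difference in those pairs combines analyser error with a capillary effect and any change between draws.

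The pooled figure blends the two in whatever proportion the site happens to produce. It then estimates neither analyser accuracy nor point-of-care performance, and another site with a different mix could get a different answer from the same device. The reference analyser and operator also tend to differ by cohort, so the results by cohort do not separate the sample types either. This matters because the study is meant to inform device placement, the preferred blood collection method and the design of a larger trial.

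**Working it through.** **1. The plan's own figures.** The stated intervals are Wilson score intervals:

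(p + z²/2n ± z·√[p(1−p)/n + z²/4n²]) / (1 + z²/n), with z = 1.96.

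For Cohort 1, 43/48 gives p = 0.8958:

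(0.8958 + 0.0400 ± 1.96 × √[0.001944 + 0.000417]) / 1.0800 = (0.9358 ± 0.0952) / 1.0800 = 77.8% to 95.5%, as section 14.1.1 states.

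For Cohort 2, 22/24 gives 74.2% to 97.7%, also as stated. The arithmetic is correct. Precision for validity is given by cohort and never by sample type, and no precision is stated for the combined concordance.

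**2. What each pair contains.**

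| | Venous aliquot | Finger prick |
|---|---|---|
| Specimen | Same tube as the laboratory | New capillary sample |
| Draw time | Same draw | Later, gap not limited |
| Local white-cell rise (14.2) | No | Yes, size not given |

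**3. Inputs that are missing.** The protocol gives no SD of paired differences (s), no capillary shift (b) and no finger-prick share (f). All three are assumptions below.

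**4. Share within the validity band.** If differences are Normal(b, s):

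P = Φ((0.2 − b)/s) − Φ((−0.2 − b)/s).

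The pooled share is f·P(finger prick) + (1 − f)·P(venous). Take b = 0 for venous and b = +0.1 for finger prick (× 10⁹/L):

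| s | Venous | Finger prick | Pooled, f = 25% | f = 50% | f = 75% |
|---|---|---|---|---|---|
| 0.05 | 100.0% | 97.7% | 99.4% | 98.9% | 98.3% |
| 0.10 | 95.4% | 84.0% | 92.6% | 89.7% | 86.9% |
| 0.20 | 68.3% | 62.5% | 66.8% | 65.4% | 63.9% |

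At s = 0.10, for example, the finger-prick share is Φ(1) − Φ(−3) = 0.8413 − 0.0013 = 0.840.

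**5. The concordance set itself.** Pairs differing by more than 0.2 count as invalid and leave the concordance. The mean difference among the pairs that remain is

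b − s·[φ((0.2 − b)/s) − φ((−0.2 − b)/s)] / P.

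For b = +0.1 and s = 0.10 this is 0.1 − 0.1 × (0.2420 − 0.0044)/0.840 = 0.072. For unshifted venous pairs it is 0. A shift of this size would therefore appear partly in the concordance and partly in the validity share.

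**6. Precision after splitting.** Pooled, 65/72 gives a Wilson interval of 81.3% to 95.2%. A stratum of 33 with 30 valid gives 76.4% to 96.9%.

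**The case against.** The strongest reply is that section 15.1 defers all quantitative analysis to the SAP, which may stratify, and that the quoted sentence sits in the sample-size section and forbids nothing. That stands in part: missing subgroup tables alone would not be a finding. But the protocol fixes a combined concordance and chooses which outcomes to split by sample type, and agreement is not among them.

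Other parts of the reply also stand:

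- The sentence in section 14.2 goes on to refer to several samples from the same finger stick. It supports a local white-cell rise and extra spread. It does not give a neutrophil shift against venous blood.
- Validity precision is planned by cohort, and Table 7 does not say that the 90% criterion pools the cohorts.
- The 0–5 hour label in Table 2 covers every day-0 column and is not a draw-to-draw gap. Section 12.1.2 asks for sampling as soon as possible.
- The study is descriptive, OLO results do not guide care, and funding is not formally tied to the criteria.

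A reader might infer that the 90% criterion passes or fails on the sample mix alone. The documents do not support that. At SD 0.05 every mix in the table passes, at SD 0.2 every mix fails, and only in between does the mix decide.

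A reader might also infer that transport limits push Cohort 1 towards finger prick. The standing-time rule in section 12.1.2 names no cohort and is conditional, so this is conjecture.

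**Conclusion.** The point holds as one of analysis and definition. Followed as written, the combined concordance mixes same-draw venous pairs with later capillary pairs in proportions that nothing fixes, and the validity share has the same weakness. Reference analyser and operator tend to vary with cohort, so the cohort results do not resolve it.

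The size is unknown. Under normal differences and an assumed +0.1 shift, the loss in the share within ±0.2 runs from about 2 percentage points (SD 0.05) to about 11 (SD 0.1), and about 6 at SD 0.2, where venous pairs already reach only 68%. Neither the shift nor the SDs come from the documents. The stated confidence intervals are correct. The change is worth making before analysis, but the point does not undermine the study's feasibility aims.

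**What to change.** In sections 14.1.1 and 15.1:

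- Report neutrophil agreement and the validity proportion separately for venous-aliquot pairs (analyser accuracy) and finger-prick pairs (point-of-care performance). Make the pooled figure secondary.
- Show results by reference laboratory descriptively.
- Define the pairing period using the draw times of both samples, and report the gap for finger-prick pairs.

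Reconcile section 6.1.1, which describes finger prick only, with section 12.1.2, which allows either sample.

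No extra patients or visits are needed, and sample type is already required for the flag and re-take comparisons in section 5.3. Both draw times must be available in the data. The price is precision: with about half the sample in each stratum the interval widens from roughly 14 points (81.3% to 95.2%) to roughly 20 (76.4% to 96.9%), and an uneven split would be worse for the smaller group. These estimates can only be descriptive. Stratified reporting also does not remove any selection in who received which sample, so the two strata should not be read as a controlled comparison.

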## 2 Synopsis

Short title	A point of care feasibility study to improve critical care pathways for chemotherapy-related sepsis.
Acronym	ADVANCE
Development phase	Feasibility
CTR Portfolio Number:	746
IRAS Number:	252236
ISRCTN:	TBA
Funder and reference	Tenovus - TIG2017-13
Funder and reference	Velindre Charitable Funds - 2018/18
Funder and reference	Sight Diagnostics UK
Trial design	Non-randomised cohort medical device feasibility study
Population	Cancer patients who present with suspected neutropenic sepsis whilst receiving chemotherapy
Investigational device	OLO-U1 System () (Sight Diagnostics UK Ltd).
Comparator device	Local high throughput lab-based device used to analyse 5 part white cell count
Trial participants	
WP1 Cohort 1: Cancer patients who present with suspected neutropenic sepsis whilst receiving chemotherapy
 
WP1 Cohort 2: Cancer patients who require repeat Full blood count prior to SACT (systemic anti-cancer therapy) ie presented with borderline neutropenia at pre-chemotherapy assessment and require re-testing the day before, or on day of, planned chemotherapy, or will be receiving palbociclib (Ibrance) therapy.
 
WP1 Cohort 3: Cancer patients receiving or who have received cytotoxic chemotherapy or radiotherapy
 
WP2: Cancer patients and carers of cancer patients
 
WP3: Healthcare workers

Planned sample size	
WP1 Total: Approach 90, recruit 72, 65 valid test results.
 
WP1 Cohort 1: Approach 60, recruit 48, 43 valid test results.
 
WP2 Cohort 2: Approach 30, recruit 24, 22 valid test results.
 
WP3 Cohort 3: Approach 24, 19 completed and returned surveys.
 
WP2 : Approach up to 20. Recruit up to 10-15 participants.
 
WP3: Approach up to 20. Recruit up to 10-15 participants.

Planned number of sites	One – Velindre Cancer Centre (VCC), Cardiff, Wales
Inclusion criteria	
WP1 Cohort 1:
 
 
1) 18 years old or over
 
2) Received cytotoxic chemotherapy or radiotherapy within the last 6 weeks and has signs and symptoms or infection and/or a temperature > 38°C or < 36°C
 
3) Admitted to any inpatient area at VCC for assessment for suspected neutropenic sepsis
 

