### **14.5 Inclusion in analysis**

Data derived from all participants in WP1-3 will be included in the analysis unless consent to do so has been specifically withdrawn on the ADVANCE Withdrawal CRF [28].

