## **15 Analysis**

### **15.1 Quantitative analysis of WP1 device cohort evaluation**

All quantitative analysis will be documented in the SAP [36] prior to implementation of the analysis.

As this is a feasibility study, statistical analysis of study outcomes will be descriptive in nature. Continuous data will be reported as means and standard deviations, or medians and interquartile ranges, as appropriate. Categorical data will be reported as frequencies and proportions. Outcomes will be estimated with their associated 95% confidence intervals.

No formal hypothesis testing will take place.

While subsequent funding is not formally linked to satisfying any specific progression criteria, we propose the following as indicators that a larger study is feasible (NB. Failure to meet one or more of the criteria would indicate that modifications are required, with potentially further feasibility testing, prior to a larger study) as described in Table 7.

**Table 7.** Trial progression criteria

Outcome	Criteria
Recruitment	At least 80% of patients approached to take part provide consent
Intervention adherence	At least 90% of recruited participants receive the OLO test
Intervention fidelity	A valid test result is obtained from at least 90% of recruited participants who receive the OLO test
Survey fidelity	A survey is completed and returned from at least 80% of recruited participants who are given the survey
Data collection	At least 80% of recruited participants have clinical outcome data available for statistical analysis
Staff focus groups	Focus group data indicates that the OLO test is acceptable
Patient focus groups	Focus group data indicates that the OLO test is acceptable

There will be no interim analyses other than TMG review of WP1 SAE's at TMG meetings, Trial Manager review of screening logs through the WP1-3 recruitment phases, and Trial Manager review of data entry after approximately half of the participants have been recruited to WP1.

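### Section 14.1.1 measures OLO–laboratory neutrophil concordance only in results already within ±0.2 × 10⁹/L of the laboratory, so the concordance estimate is circular

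*Protocol*

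**What the plan says.** The primary outcome (section 5.2) is the neutrophil count from OLO and from the standard laboratory full blood count. How the two are compared is stated in section 14.1.1, for Cohorts 1 and 2 combined. Concordance is evaluated "across all patients with a valid output. A valid OLO neutrophil result will be one which produces a test result which is within" (a margin of ±0.2 × 10⁹/L around the standard laboratory result).

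Section 5.3 uses the same definition for a secondary outcome: "A valid result is when the OLO system neutrophil result is" ±0.2 × 10⁹/L of the laboratory gold standard. Table 7 in section 15.1 makes it a progression criterion: "A valid test result is obtained from at least 90% of recruited participants who receive the OLO test". The synopsis plans on it: "WP1 Total: Approach 90, recruit 72, 65 valid test results".

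Section 14.5 points the other way: "Data derived from all participants in WP1-3 will be included in the analysis unless consent to do so has been specifically withdrawn". Section 15.1 says the analysis is descriptive, with 95% confidence intervals and no hypothesis tests.

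**The concern.** The word *valid* would normally mean that the analyser produced a usable count. Here it means that the count agrees with the comparator. Restricting a concordance analysis to such results removes the disagreement before it is measured.

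The primary objective is to evaluate OLO against the laboratory device, and the lay summary presents OLO as a way of ruling out a low white cell count. The size and direction of its errors are therefore what the larger trial needs to know. Section 4.1 describes neutropenic sepsis at a neutrophil count of 0.5 × 10⁹/L or below. A laboratory count of 0.5 or below paired with an OLO count above 0.7 differs by more than 0.2, so that pair is left out of the concordance estimate.

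**Working it through.** **The plan's own figures.** Section 14.1.1 gives 95% intervals for the valid proportion, and these reproduce as Wilson score intervals, with centre (x + z²/2)/(n + z²) and half-width z/(n + z²) × √(np(1−p) + z²/4).
- Cohort 1, 43 of 48: centre 44.92/51.84 = 0.8665; half-width (1.96/51.84) × √(4.479 + 0.960) = 0.0882; interval 77.8% to 95.5%, as stated.
- Cohort 2, 22 of 24: 74.2% to 97.7%, as stated.
- Total: 43 + 22 = 65, as in the synopsis.

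These intervals are sound and the point does not affect them.

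**Bounds that need no distribution.** Let d = OLO − laboratory, and keep a pair only if |d| ≤ 0.2. Then |mean d| ≤ 0.2 and SD(d) ≤ √(0.2² − mean²) ≤ 0.2. The limits mean ± 1.96 SD cannot lie further from zero than 0.2 × √(1 + 1.96²) = 0.44, however the device performs.

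**Size under assumed normal differences.** The protocol gives no bias or SD, so the values below are assumptions. With bias μ, SD σ, a = (−0.2 − μ)/σ and b = (0.2 − μ)/σ:
- share kept P = Φ(b) − Φ(a)
- apparent mean = μ + σ[φ(a) − φ(b)]/P
- apparent variance = σ²{1 + [aφ(a) − bφ(b)]/P − ([φ(a) − φ(b)]/P)²}

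For μ = 0 and σ = 1.0: P = 2Φ(0.2) − 1 = 0.159; variance = 1 − 0.4 × 0.391/0.1585 = 0.0133; SD = 0.115; limits ±1.96 × 0.115 = ±0.23.

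| Assumed bias, SD | Pairs kept | True 95% limits | Apparent bias | Apparent 95% limits |
|---|---|---|---|---|
| 0, 0.1 | 95% | ±0.20 | 0 | ±0.17 |
| 0.3, 0.5 | 26% | −0.68 to +1.28 | 0.02 | −0.21 to +0.24 |
| 0, 1.0 | 16% | ±1.96 | 0 | ±0.23 |

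The true limits span a tenfold range of SD, while the apparent limits hardly move.

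**A device unrelated to the laboratory.** A simulation of 2 million pairs took both counts as independent and uniform on 0–2 × 10⁹/L (an assumption). Lin's concordance coefficient was 0.00 on all pairs and 0.98 on the 19% within ±0.2.

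**Where poor performance does show.** It shows in the share kept, which is the protocol's valid proportion. With no bias, 90% within ±0.2 requires an SD of about 0.2/1.645 = 0.12. At SD 1.0 the share is 16%, far below the 90% criterion.

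**The case against.** **Other outcomes would reveal a poor device.** This is right, and it limits the point. A reader might infer that the trial as a whole cannot tell a good device from a useless one. The documents do not support that. The valid proportion is a secondary outcome and carries a 90% criterion. Section 5.3 also counts discrepancies that would have changed management on retrospective clinical review, and section 12.1.6 provides for the consultant to see the OLO result afterwards.

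**Technical failure is recorded separately.** A reader might infer that device failure cannot be told from disagreement. Section 5.3 lists flags, error codes and re-takes as outcomes, section 11.4 provides database fields for them, and Table 7 has its own row for receiving the test.

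**Not every threshold error is dropped.** A laboratory count of 0.45 with an OLO count of 0.60 crosses 0.5 but differs by 0.15, so it is kept. Those that are dropped can still appear in the discrepancy count.

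**The wording may be loose, or the SAP may settle it.** The sentence sits under sample size, section 15.1 carries no such restriction, and section 14.5 includes everyone. The intention may have been the share within ±0.2 among patients with any output. The text does not secure that reading: the definition follows immediately and is repeated in section 5.3. Section 14.5 is a general rule about consent, so it needs reconciling with 14.1.1 but does not override it. This is also not a detail left to the SAP, since the protocol states an analysis set and a SAP faithful to it would inherit the fault.

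**It is a descriptive feasibility study, and OLO results do not guide care.** Both are true. A descriptive estimate must still describe the device.

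**Conclusion.** The point holds for the concordance analysis and should be corrected before that analysis is run. As written, the comparison stated for the primary outcome is selected on the quantity it estimates, and it cannot show large bias or wide scatter. That much follows from the definition alone. The illustrative size (limits of about ±0.23 reported where ±1.96 is true, with 16% of pairs kept) rests on assumed normal differences with SD 1.0 and no bias.

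The measures that survive show that a device disagrees, and how often. They do not give the size and direction of disagreement, which is what the concordance analysis is for. A reader might also infer that Table 7's fidelity row should be changed to technical success. The documents do not call for that. It is the only quantitative accuracy benchmark among the progression criteria, and without it a device that always returned a wrong number could pass.

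**What to change.** 1. In section 14.1.1, evaluate concordance on every participant with a numeric OLO neutrophil count and a laboratory count, in line with section 14.5. Mean difference and limits of agreement with 95% confidence intervals would serve.
2. State that a result is not excluded merely because it is flagged as outside the normal range. Section 14.2 says the analyser flags such values, so excluding them could remove the neutropenic patients the study is about.
3. Keep within ±0.2 × 10⁹/L as a separately named agreement proportion over all those pairs. Keep it as the 90% criterion in Table 7, renamed so that it is not read as technical success.
4. Align the synopsis (the 65 valid results), section 5.3, section 14.1.1 and Table 7, and state the denominator each time: section 5.3 now uses all recruited participants and Table 7 those who receive the test. The haemoglobin, platelet and lymphocyte margins in section 5.3 use the same word and should take the new name.

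The cost is wording in the protocol and matching text in the SAP, with no new data, patients or procedures. Reported agreement may look less favourable.
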